2. Secondary (comparison of each listed parameter between the prospective treatment groups in addition to comparison of each treatment group with historic controls):
 - a. Growth (rate of change)

- i. Weight, length, and head circumference at enrollment, on a weekly basis while receiving study lipid, and 2-3 weeks post-study lipid completion.
- ii. Weight, length, and head circumference at 36 weeks corrected gestational age and time of discharge.
- b. Essential fatty acid profile differences and development of deficiency
- c. Average total caloric intake for all patients on weekly basis
 - i. Average lipid dose delivered on weekly basis
- d. Feeding tolerance/ percentage of total calories from enteral feeds
 - i. Time to achievement of enteral autonomy (full enteral feedings)
 - ii. Percentage of enteral calories at end of study
 - iii. Percentage of patients in each group with enteral autonomy
- e. Transaminase, alkaline phosphatase, GGT levels at enrollment, every 4 week time point, and end of study
- f. Triglyceride concentration at baseline, weekly, and end of study
- g. Rates of other diagnoses in each study group
 - i. Retinopathy of prematurity as diagnosed by Ophthalmologic examination
 - ii. Chronic lung disease as defined by need for oxygen at time of discharge or 36 weeks corrected gestational age (if at least 28 days of age), whichever comes first.
- h. Rates of adverse and serious adverse events in each group
- i. Length of stay
- j. Two year neurodevelopmental differences using ASQ-3 screening

Study Population

Inclusion criteria

Infants admitted to the Riley Hospital Neonatal Intensive Care Unit (NICU), regardless of postmenstrual or corrected gestational age, with anticipated need for parenteral nutrition for four or more weeks PLUS one or more of the additional inclusion criteria listed below will be eligible for inclusion within the study and for randomization. Inclusion criteria include:

- Anatomic intestinal defect: Neonate with intestinal atresia, omphalocele, gastroschisis or volvulus with or without intestinal resection and need for parenteral nutrition pre or post-operatively.
- Ischemic/perforation intestinal injury: Neonates with spontaneous intestinal perforation or necrotizing enterocolitis requiring surgical intervention with need for parenteral nutrition post-operatively.

Exclusion criteria at time of study enrollment

- Infant with current weight less than 750 grams

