 - i. Each patient's chart will be reviewed for documentation of retinopathy of prematurity or bronchopulmonary dysplasia (chronic lung disease). The absence or presence of these diseases at the time of discharge will be noted for each study patient, particularly those patients born prematurely at less than 37 weeks gestation.
- d. Length of Stay:
 - i. An ICU length of stay will be calculated for each patient based on their admit date and discharge date from the Riley NICU.
 - ii. For patients transferred to another unit prior to discharge the transfer date will also be documented. For these patients a NICU length of stay and total hospital length of stay will be calculated.
- e. Laboratory monitoring (see Table 2 below for reference schedule):
 - i. Effort will be made to draw all study lab tests along with other standard of care, routinely scheduled labs.
 - ii. The schedule outlined here is a schedule of minimum laboratory work to be obtained. These studies may be obtained more often by the patient's primary clinical team. Any lab test obtained by the primary team within 3 days for weekly labs or within one week for less frequent labs will be used in place of the research lab test.
 - iii. Of note all lab tests listed could be considered standard of care, with the exception of INR.
 - iv. Essential fatty acid profiles will be obtained every 4 weeks (28 days) while receiving study lipid regimen.
 - 1. Blood volume needed 0.3-1mL
 - 2. Considered standard of care in any patient on alternative lipid dosing, such as patients enrolled in this study.
 - 3. If diagnosed with essential fatty acid disorder, defined as triene:tetraene ratio >0.05:
 - a. If Smoflipid dose is less than 3 g/kg/d, SMOF will be increased by 0.5 g/kg/d or to 3 g/kg/d maximum
 - b. Those receiving Smoflipid at 3 g/kg/d will be changed to Intralipid at current Smoflipid dose
 - c. Those receiving Intralipid will have their dose increased by 0.5 g/kg/d to maximum of 3 g/kg/d
 - v. Total and fractionated bilirubin levels will be monitored at least once weekly (7 days)
 - vi. Liver function panel and gamma-glutamyl transferase (GGT) will be monitored at least every 2 weeks (14 days).
 - vii. Triglyceride levels will be monitored within the first 48 hours of lipid initiation and then once weekly (7 days).

1. If triglyceride level >250 mg/dL will decrease dose of study lipid by 1g/kg/d to minimum of 2 g/kg/d of Smoflipid or 1 g/kg/d three days per week for Intralipid

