- iv. Subjects leaving the study secondary to parental request may not have further follow-up performed if at the request of the parent.

Historic Controls

Historic controls will have their charts reviewed to document the same information as for prospective patients. For historic controls, this information will be limited to their time admitted to Riley Hospital only. Information recorded will include:

- 1. Diagnosis and procedures:
 - a. Documentation of diagnosis making eligible for study participation
 - b. Documentation of surgery performed
- 2. Parenteral nutrition:
 - a. Length of parenteral nutrition: Documentation of total days of parenteral nutrition including start date, stop date, and dates not receiving parenteral nutrition.
 - b. Lipid dosing: maximum lipid dose, average lipid dose on weekly basis
 - c. Glucose dosing: documentation of glucose infusion rate (GIR) including maximum dose and weekly average GIR dose
 - d. Protein dosing: documentation of maximum amino acid dose received and weekly average amino acid dose
 - e. Discontinuation of parenteral nutrition: including reason for discontinuing and for what length of time.
- 3. Enteral Feeding:
 - a. Autonomy: the time from start of enteral feeding until complete enteral autonomy (enteral feeding only) will be documented for each patient.
 - b. Weekly enteral feeding: On a weekly basis an average of enteral feeding intake will be determined both in volume and calories. Based on these calculations a percentage of overall intake related to parenteral nutrition will be determined.

- c. Milk intake: The particular milk prescribed to each patient will be documented along with the particular form of additives and fortification used.
- 4. Measurements:
 - a. Weight, length, and head circumference will be recorded on a weekly basis for each patient.
 - b. Corrected measurements will also be obtained for each patient at 36 weeks corrected gestational age and the time of discharge from the Riley NICU. Given these are historic patients, the values obtain closest to these dates will be used for the purposes of this study.
- 5. Laboratory values:
 - a. Laboratory values listed above for prospective patients will be documented for historic patients if available within the electronic medical record.
 - b. If cholestasis is diagnosed the interventions and treatments received by the patients will be documented.
- 6. Diagnoses of prematurity

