 - a. Patients born less than 37 weeks will also have their chart reviewed for documentation of retinopathy of prematurity and bronchopulmonary dysplasia or chronic lung disease. Presence or absence of these diagnoses will be documented.
- 7. Length of stay:
 - a. The admit date and discharge date from the Riley NICU will be documented and a length of calculated for each patient.
 - b. For patients transferred from the Riley NICU to the floor the transfer date and discharge date from the hospital will also be documented and a NICU length of stay and overall hospital length of stay will be documented.
- 8. Neurologic Follow-up:
 - a. Any patient that has an ASQ-3 performed during year 2 of life will have this information documented.
 - i. This is not required to be included in the study and will only be documented if information is available.

Study Duration

Patients will continue to receive study lipid until one of the following points, whichever should come first:

1. The maximum time for receiving study lipid per the study team will be 12 weeks (84 days).
2. Cholestasis with direct bilirubin of ≥ 3 mg/dL on two consecutive lab draws at least 5-7 days apart.
3. Lipid or parenteral nutrition discontinuation for more than one week (7 days).
4. Discharge home or transfer to another facility outside of Riley Hospital for Children.

Once one of these parameters are met, as noted previously, the lipid dosing would be at the discretion of the patient's primary physician. The patient will remain in the study to have follow-up laboratory, growth, and neurodevelopmental information collected.

Adverse Events and Serious Adverse Events

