All patients will be monitored on a daily basis for the development of any adverse events (AE) from the start of the study lipid until one week (7 days) after leaving the study. An adverse event is defined as any untoward medical occurrence in a research subject temporally associated with the use of the study drug, whether or not it is related to the drug. Any worsening of a pre-existing condition or illness is considered an adverse event. This includes pre-existing and or new clinical conditions or morbidities associated with prematurity or the patient's underlying diagnoses. Laboratory abnormalities or vital sign changes are considered adverse events only if they meet the specific criteria listed in the table below. A serious adverse event (SAE) is an AE that leads to death of a subject, life-threatening event, persistent or significant disability, or an important medical event requiring medical or surgical intervention to prevent a serious outcome.

Many possible AE and SAE are listed in Table 3 below. Patients will be monitored continuously by one of the principal investigators, [name] or [name], for possible AEs and SAEs. Clinical significance and relation to the study will be determined by [name] and/or [name] based on best medical judgement. Unanticipated events that are determined to be an AE related or possibly related to the research drug will be promptly reported to the IRB by [name] or [name] within 5 business days. Major protocol issues, including drug administration issues or errors, will also be reported to the IRB within 48 hours. Events that are determined to be an SAE or lead to death of a patient will be promptly reported to the IRB within 24 hours.

A separate Data and Safety Monitoring Committee (DSMC) will be used to monitor patient outcomes and AE along with SAE events. The DSMC members will not include the primary investigation team and will be made up of other experts from Neonatology ([name]), Pediatric General Surgery ([name]), Pediatric Gastroenterology ([name]), and Statistics. The DSMC will meet within 2 weeks following enrollment of the first 10 patients. Further enrollment will be put on hold pending initial DSMC review. If no safety concerns are found by independent DSMC review, patient enrollment will proceed. DSMC will meet subsequently every 6 months for the duration of the study.

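### Fatty acids, adverse events and ASQ-3 are to be compared with historic controls in whom they are not ascertained comparably, so these contrasts carry a high risk of differential ascertainment bias

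*Combined protocol and SAP*

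**What the plan says.** Study Objectives, item 2 (Secondary), sets the scope for every secondary parameter: "comparison of each listed parameter between the prospective treatment groups in addition to comparison of each treatment group with historic controls". Three of the parameters under it are b, "Essential fatty acid profile differences and development of deficiency"; h, "Rates of adverse and serious adverse events in each group"; and j, "Two year neurodevelopmental differences using ASQ-3 screening".

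For prospective infants, collection is scheduled:

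- Adverse events: "All patients will be monitored on a daily basis for the development of any adverse events", from the start of study lipid until 7 days after leaving the study, graded against Table 3 (Adverse Events and Serious Adverse Events).
- Fatty acids: a profile every 28 days on study lipid (Study Procedures 3.e.iv). Testing is described there as "Considered standard of care in any patient on alternative lipid dosing, such as patients enrolled in this study".
- ASQ-3: obtained for all prospective infants (Study Procedures 3.f).

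For the 24 controls, the data-collection section headed Historic Controls opens by saying that charts will be reviewed for the same information, limited to the Riley admission. It then lists eight items, none of which is adverse events. Item 5 reads "Laboratory values listed above for prospective patients will be documented for historic patients if available within the electronic medical record". Item 8, on a control's ASQ-3, reads "This is not required to be included in the study and will only be documented if information is available".

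Statistical Considerations names adverse events and fatty-acid deficiency among the categorical outcomes. It assigns Fisher's exact test between groups at the 5% level, without limiting this to the randomised arms.

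**The concern.** A contrast between a group watched daily and a group read from old charts measures how hard each was watched as well as what was given. If charts miss events, controls will appear to have had fewer, and both study strategies will look less safe than standard-dose soy lipid. If control infants were tested for fatty acids or development more often when something seemed wrong, the tested controls will look worse than the cohort they came from, and the study strategies will look better. Neither result would be a treatment effect, and the two errors pull in opposite directions.

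This is a pilot meant to inform a larger study. A spurious safety signal, or a spurious benefit on deficiency or development, could affect which strategy is taken forward. The plan contains no method for retrieving adverse events from charts, no rule for missing control values and no caution on interpreting these contrasts.

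**Working it through.** **Ascertainment side by side**

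| Item | Prospective arms | Historic controls |
|---|---|---|
| h. Adverse events | Daily, against Table 3; window runs from start of study lipid to 7 days after leaving the study | General promise of the same information; no adverse-event item, window or retrieval method |
| b. Fatty acids | Every 28 days on study lipid | If in the electronic record; controls are defined by standard dosing, whereas testing is called standard of care for alternative dosing |
| j. ASQ-3 | All infants | Only if one was done; not required |

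Three further points bear on this.

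- The adverse-event definition does not carry over. An event is defined by its timing relative to the study drug, and Table 3 grades pulmonary deterioration during study drug infusion. Controls have no study drug. The DSMC's adverse-event review (Study Stopping Criteria) covers only the prospective populations.
- INR defines the coagulation event in Table 3. It is also the one listed test that Study Procedures 3.e.iii excludes from standard of care. Prospective infants have it on schedule; controls have it only if it is in the record.
- Limiting control information to the Riley admission sits badly with an ASQ-3 at two years.

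**What unequal ascertainment could do**

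The plan gives no event rate, effect size or power for these contrasts, so there is no figure of its own to reproduce. The group sizes (25 per arm as target, 12 as minimum, 24 controls), the test and the 5% level come from the protocol. A two-sided test is assumed because sidedness is not stated. True rates, capture and testing probabilities are assumptions.

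*Adverse events.* Let the true proportion of infants with an event be p in both groups, and let charts capture a fraction c. The expected control proportion is then p × c; for example, 0.40 × 0.50 = 0.20. Summing exact binomial probabilities over all tables in which Fisher's test gives P ≤ 0.05 yields these false-positive rates:

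| Prospective n v 24 | Capture c | p = 20% | 40% | 60% | 80% |
|---|---|---|---|---|---|
| 25 | 100% | 3.2% | 4.0% | 4.0% | 3.2% |
| 25 | 80% | 3.8% | 6.5% | 12.4% | 19.5% |
| 25 | 50% | 9.3% | 25.1% | 54.2% | 82.5% |
| 12 | 50% | 10.4% | 17.6% | 30.1% | 57.8% |

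With full capture the test keeps its level. With 80% capture and a rare event, little happens. The error is large when events are common and capture is poor.

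*Fatty-acid deficiency.* Let the true rate be p = 10% in both groups. Let s1 be the chance that an affected control was tested and s0 the chance for an unaffected one. The observed rate among those tested is p·s1 / [p·s1 + (1 − p)·s0], and the expected number tested is 24 × the denominator.

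- s1 = s0 = 50%: 0.05/0.50 = 10%, 12 tested; rejection against 25 is 1.5%. No bias, but half the controls are lost.
- 80% and 40%: 0.08/0.44 = 18%, about 11 tested; rejection 6.6%.
- 80% and 20%: 0.08/0.26 = 31%, about 6 tested; rejection 20.2%.
- 60% and 10%: 0.06/0.15 = 40%, about 4 tested; rejection 25.8%.

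*ASQ-3.* The same formula, with an assumed 30% truly below the cut-off and 20% of unaffected controls screened:

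- equal screening (20%): 0.06/0.20 = 30%, unchanged;
- 40% of affected screened: 0.12/0.26 = 46%;
- 60% of affected screened: 0.18/0.32 = 56%.

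**The case against.** The strongest reply is that Historic Controls opens by promising the same information as for prospective infants, and the list that follows is not worded as exhaustive. Many Table 3 events can be rebuilt from a chart: glucose, liver enzymes, triglycerides, platelets, treated positive blood cultures and imaged thrombus, as well as death. A reader might infer from the missing list item that control adverse events are absent by design. The documents do not support that: they leave it unclear whether and how such events will be collected. The promise nevertheless supplies no window or method, and retrospective reading cannot reproduce daily surveillance.

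A reader might also infer that control fatty-acid and ASQ-3 results exist only because someone was worried. The documents do not say so. For fatty acids they support less testing in controls, which makes selective testing plausible but unproven. For ASQ-3 they give no reason for testing, and routine follow-up fits equally well.

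Nor is there a demonstrated mismatch in ASQ-3 age. Study Procedures 3.f defines the second year of life as 2 years 0 days to 2 years 364 days, and the control item uses similar wording, so the windows can match. Statistical Considerations also names no test for ASQ-3, which softens that limb, although Objective 2 still promises the comparison.

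Finally, no randomised arm receives standard-dose soy lipid, so controls are the only safety reference for that regimen. Dropping every control comparison under h would discard events that charts record well. That objection stands, and the fix allows for it.

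**Conclusion.** The point holds as a high risk of differential ascertainment bias in items b, h and j against historic controls. It would go too far to call these contrasts biased by construction. Unequal ascertainment is built into the plan, but bias follows only if chart capture is incomplete or testing is selective; missingness at random would cost precision alone.

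The likely direction is against the study strategies for adverse events. For fatty acids and ASQ-3, selective testing could make controls look worse; for ASQ-3 the documents give no basis for saying whether testing was selective. The size is unknown. The figures above show what assumed capture and testing rates would produce and are not estimates for this cohort.

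The randomised comparison of the two arms and the primary cholestasis endpoint are not touched by this point.

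**What to change.** In Objective 2 and in Statistical Considerations, state that formal tests of items b, h and j are limited to the two randomised arms. Report control values for these items descriptively, giving the number of controls assessed, with no test.

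A formal control comparison under h may be kept only for events that charts capture in the same way in all groups, such as death, culture-positive infection and imaging-confirmed thrombosis. Define them identically in all groups and over the same window, with a start point that does not depend on study lipid.

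The cost is a sentence or two in each section, plus a short event definition if the exception is used. What is lost is the formal historic-control test for the remaining b, h and j items. The randomised comparison loses nothing.

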- AST or ALT greater than 5 times the upper limit of normal within 2 weeks of enrollment

- Direct bilirubin greater than 2 mg/dL on any consecutive measurement 5-7 days apart within 2 weeks of enrollment
- Severe coagulopathy with elevated INR greater than 2.0 or clinically significant bleeding as determined by the primary and research teams
- Culture confirmed sepsis with positive blood, urine, or CSF culture within 2 weeks (14 days) of enrollment
- Renal failure requiring dialysis
- Cyanotic heart disease requiring prostaglandin therapy
- Hypertriglyceridemia (greater than 250mg/dL) at time of enrollment

Enrollment/Randomization

A maximum total of 50 prospective patients, 25 per arm, will be enrolled in the study. Patients will be eligible for enrollment if they meet the above listed enrollment criteria. Once patients are determined to meet enrollment criteria, the parents of the patient will be approached and informed consent will be obtained. Please see separate informed consent document for full consent details.

Stratified randomization will be used to divide patients into each treatment group. Patients will be initially stratified based on the diagnosis of necrotizing enterocolitis or spontaneous intestinal perforation (ischemic/perforation group) or anatomic intestinal abnormality. Once stratified based on diagnosis, patients in each stratum will then be randomized to receive either Smoflipid or Intralipid reduction as described below. Group randomization will be based on premade concealed envelopes.

This study will not be blinded as the caloric dose of the lipid strategies will vary and potentially influence other TPN dosing. Both IV lipids will be given as a solution separate from the remaining TPN. This separate IV lipid will be given as two 12 hour infusions over a 24 hour period.

In the event of slower than anticipated patient enrollment, a minimum of 24 patients (12 per treatment group) will be enrolled in order to obtain needed feasibility data.

Historic Controls

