1) Individual Patient Stopping Criteria:

- a) Development of progressive cholestasis as defined by direct bilirubin of 3 mg/dL or greater on two separate lab draws 5 to 7 days apart.
- b) Clinically significant laboratory abnormalities that change the clinical course of the patient, or the patient's care and are deemed related to the study drug by the primary investigators ([name] or [name]). The laboratory abnormalities include, but are limited to:
 - i) Change in liver function with AST or ALT greater than 5 times the upper limit of normal or GGT greater than 3 times the upper limit of normal for patient age.
 - ii) Creatinine greater than 2 times upper limit of normal for patient age.
 - iii) Clinically significant coagulopathy with INR greater than 2.5 or INR greater than 1.5 and clinically significant bleeding.
 - iv) Clinically significant thrombocytopenia with platelet count less than 30 or less than 50 with bleeding.
 - v) Persistent hyperglycemia with glucose greater than 200 mg/dL despite changes in parenteral nutrition glucose infusion rate.
 - (1) Inability to tolerate appropriate calorie intake due to elevated glucose infusion rate that may be required with lipid reduction.
 - vi) Persistent hypertriglyceridemia (on 3 or more lab draws each at least 24 hours apart) greater than 250 mg/dL despite decreasing or holding lipid dose.
- c) At the request of the parent or legal guardian.
- d) At the request or recommendation of the patient's primary physician and care team.

If the patient is withdrawn from the study, treatment including parenteral nutrition administration and macronutrient content will be provided at the discretion of the primary faculty physician providing patient care.

2) Study Stopping Criteria:

- a) DSMC or primary investigator initiated study cessation:
 - i) As noted a Data Safety and Monitoring Committee (DSMC) of experts from Neonatology, Gastroenterology, Surgery and Statistics will meet within 2 weeks of the first 10 subjects and following at least every six months during the remainder of the study period. They will review patient recruit, patient outcomes, and adverse events in both prospective patient populations. Significant patient safety concerns will

be determined by the DSMC. These patient concerns include, but are limited to, finding a significant amount of AE or SAE within one study group or a large difference in outcomes between study treatment arms.

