- ii) In adequate patient recruitment. We anticipate recruiting an average of 4 patients per study month. If there is a significant lag and will be unable to obtain our full number of patients within a reasonable time, this will be reason to terminate the study early.
- b) Principle investigators will consider study cessation if SAEs occur within a specific treatment arm out of proportion to what would be expected from typical disease course.

Statistical Considerations

Our goal is to recruit 25 patients into each group. Given this is a pilot study, the minimum number needed per arm would be 12 patients as per published statistician recommendations [21]. The reasoning for using a pilot study include determining the feasibility of performing a larger scale study. Performing a pilot study prior to the large-scale study will give us information on patient recruitment and retention, along with design flaws that may be remedied prior to future studies.

All data will be summarized by group at each time point; summaries will include frequencies and proportions for categorical variables and mean, standard deviation, and range for continuous variables. Distributions of continuous variables will be examined. Parenteral nutrition characteristics will be recorded and tabulated. Tabulated categorical outcomes will include: proportions of subjects with cholestasis or IFALD, essential fatty acid deficiency, enteral autonomy at end of study, retinopathy of prematurity, chronic lung disease, and adverse events. Tabulated continuous measurements will include: growth rates, essential fatty acid profile, total caloric intake, percentage of calories from enteral intake, time to enteral autonomy, lipid dose delivered, bilirubin level, liver enzymes, gamma-glutamyl transferase (GGT), triglycerides, and length of stay. Fisher's Exact Tests will be used to compare between groups for categorical variables. Time to enteral autonomy will be evaluated using Kaplan-Meier survival curves and a log-rank test. Mixed models will be used to compare between groups and compare within groups over time for continuous variables measured throughout the study. Length of stay will be compared using a Wilcoxon Rank Sum test. A 5% significance level will be used for all tests mentioned.

Privacy/Confidentiality Issues

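### The enteral share of total calories carries the randomised lipid dose in its denominator, so it can differ between groups at identical enteral intake when glucose does not fill the calorie gap

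*Combined protocol and SAP*

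**What the plan says.** Study Objectives 2.d names the outcome "Feeding tolerance/ percentage of total calories from enteral feeds". It has three sub-measures. One, 2.d.ii, is a calorie share: "Percentage of enteral calories at end of study". The other two are time to full enteral feeding (2.d.i) and "Percentage of patients in each group with enteral autonomy" (2.d.iii). Statistical Considerations lists "percentage of calories from enteral intake" among the continuous measurements and assigns mixed models to continuous variables followed through the study. It lists no absolute enteral intake.

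Lipid dose is the randomised factor. Smoflipid rises to a goal maximum of 3 g/kg/d and is then weaned to 0 by Table 1 as feeds advance. Reduced Intralipid stays at 1 g/kg/d while parenteral nutrition continues, unless clinical concerns or caloric need lead to a change. Historic controls received 2-3 g/kg/d. In both arms glucose is to supply the non-protein calories still needed, up to 16 mg/kg/min (Study Procedures 1.c and 2.a.ii).

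Three further passages bear on whether that replacement succeeds:
- Enrollment/Randomization explains the open-label design by saying that "the caloric dose of the lipid strategies will vary and potentially influence other TPN dosing".
- Study Procedures 3.e.ix has the primary team consider lowering the glucose rate after repeated readings above 200 mg/dL.
- Criteria for Stopping Study 1.b.v lists "Inability to tolerate appropriate calorie intake due to elevated glucose infusion rate that may be required with lipid reduction".

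For historic controls the chart review states: "On a weekly basis an average of enteral feeding intake will be determined both in volume and calories". That review is described as collecting the same information as for prospective patients.

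**The concern.** A share of total calories moves when either part moves. Here the parenteral part contains the treatment under test. If an infant on reduced lipid does not receive the missing calories as glucose, the total falls and the enteral percentage rises with no more milk taken. Where the Smoflipid arm has been weaned below 1 g/kg/d, the same mechanism works in the other direction. A group difference in the tested variable could then be read as better or worse feeding tolerance when enteral intake was the same. The comparison of reduced Intralipid with historic controls is exposed in the same way.

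**Working it through.** The plan states no effect size, standard deviation or power for this outcome, so there is no figure of its own to reproduce.

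**Inputs from the documents.** Lipid doses and enteral calories come from Table 1 (Smoflipid) and Study Procedures 2.a (1 g/kg/d). Total calories can be inferred from Table 1 as enteral calories / (1 − parenteral share): 40/0.4 = 50/0.5 = 60/0.6 = 70/0.7 = 100 kcal/kg/d. The outer row edges give more: 30/0.2 = 150 and 90/0.8 = 112.5.

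**Assumptions not in the documents.** Lipid supplies k = 10 kcal/g (range 9-11), dextrose 3.4 kcal/g and amino acid 4 kcal/g. The fraction f of the lipid calorie gap that glucose replaces is varied.

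**Step 1: artefact at equal enteral intake.** Let E be enteral calories, T = 100 the Smoflipid-arm total, L the Table 1 lipid dose, and d = (L − 1) × k. The difference in share, reduced Intralipid minus Smoflipid, is

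E / (T − d(1 − f)) − E / T.

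| E (kcal/kg/d) | Lipid, g/kg/d (Smoflipid v Intralipid) | f = 0 | f = 0.5 | f = 1 |
|---|---|---|---|---|
| 30 | 3 v 1 | 30/80 − 30/100 = +7.5 | +3.3 | 0 |
| 40 | 3 v 1 | 40/80 − 40/100 = +10.0 | +4.4 | 0 |
| 45 | 2.5 v 1 | 45/85 − 45/100 = +7.9 | +3.6 | 0 |
| 55 | 2 v 1 | 55/90 − 55/100 = +6.1 | +2.9 | 0 |
| 65 | 1.5 v 1 | 65/95 − 65/100 = +3.4 | +1.7 | 0 |
| 80 | 1 v 1 | 0 | 0 | 0 |
| 90 | 0 v 1 | 90/110 − 90/100 = −8.2 | −4.3 | 0 |

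Results are in percentage points. With k from 9 to 11 and f = 0, the largest positive value is +8.8 to +11.3 and the negative value is −7.4 to −8.9. Two rows sit on Table 1 boundaries. At 40 kcal with 2.5 g/kg/d the result is 40/85 − 40/100 = +7.1, and the 0 v 1 contrast applies only above 90 kcal. Using the outer-edge totals shrinks the values: 30/130 − 30/150 = +3.1 and 90/122.5 − 90/112.5 = −6.5.

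**Step 2: historic controls.** At E = 40 and T = 100 in controls, reduced Intralipid against 2 g/kg/d gives 40/90 − 40/100 = +4.4 with no replacement. Against 3 g/kg/d it gives +10.0. The documents give no weaning schedule for controls, so this cannot be followed along the table.

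**Step 3: does the glucose cap prevent replacement?** At E = 30 and T = 100, the reduced arm needs 100 − 30 − 10 = 60 kcal/kg/d from glucose and amino acid. If glucose supplied all of it, the rate would be 60/3.4 × 1000/1440 = 12.3 mg/kg/min. With amino acid at 3-4 g/kg/d (12-16 kcal), it is 48/3.4 × 1000/1440 = 9.8 down to 44/3.4 × 1000/1440 = 9.0. All are below 16, so the cap does not bind here. Replacement would fail through glucose intolerance or departure from the rule.

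**Step 4: the alternative measure.** With E itself as the outcome, the difference at equal enteral intake is 0 whatever the lipid dose or f.

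**The case against.** The strongest reply is that the plan directs glucose to fill the gap, and that full replacement leaves no artefact. That stands. A reader might infer from the randomisation section that the protocol expects a calorie deficit under lipid reduction. It does not say so: it says the lipid calories differ and may alter other components, which describes compensation. A reader might also take the 16 mg/kg/min cap as proof of a shortfall, but Step 3 shows room below it. The stopping criterion and the discretion to raise Intralipid would shorten an uncorrected deficit. They show that failure is foreseen, not that it is usual, and the documents give no frequency.

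It is also fair to say that weekly total calories and lipid dose are compared under 2.c, so a reader could notice a denominator difference. That helps interpretation, but the share remains the variable tested.

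Finally, the share is a legitimate measure of dependence on parenteral nutrition, and Table 1 is itself indexed by the parenteral percentage. That stands too, and is a reason to keep it. It does not make the share a measure of how much feed the infant tolerates.

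**Conclusion.** The point holds in conditional form. The 2.d heading measure, 2.d.ii and the share listed in Statistical Considerations can differ between groups at identical enteral intake whenever glucose replacement is incomplete. With 10 kcal/g lipid and 100 kcal/kg/d total, the range is about +10 to −8 points with no replacement, roughly half that with half replacement, and 0 with full replacement. The no-replacement values are bounds, not expected values; the achieved fraction is unknown.

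A reader might conclude that lipid restriction always flatters feeding tolerance, or that a less well nourished infant always scores better. Table 1 does not support that: the artefact is zero at 1 v 1 g/kg/d and reverses once Smoflipid reaches 0, which may matter for an end-of-study value in infants near full feeds. Nor is feeding tolerance as a whole affected, since 2.d.i and 2.d.iii are not calorie shares. The consequence is one of interpretation, for part of one secondary objective in a pilot.

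**What to change.** In Study Objectives 2.d and Statistical Considerations, add weekly absolute enteral intake, in kcal/kg/d and mL/kg/d, as the feeding-tolerance measure. Compare it in the planned mixed model for both arms and the historic controls. Keep the enteral share, described as dependence on parenteral nutrition, and report it beside the weekly total calories and lipid dose of 2.c.

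The cost is one more analysed outcome, in two units, and a change of wording. Weekly enteral volume and calories are stated explicitly for controls and only by implication for prospective patients, so one sentence should confirm the collection for both arms. Absolute intake removes the denominator problem only: feeds are advanced at physician discretion in an open-label trial, so it is not a pure measure of tolerance either. No change to dosing or feeding rules is proposed.
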